24.5 Primary outcome

The primary outcome of the study is absolute difference in rejection rates (clinical or biopsy) at 12 months post randomisation. The absolute risk difference, and corresponding 95% CIs, will be obtained from a mixed-effects Cox proportional hazards models, including treatment and adjusted for centre as a random effect, analysing time to first lung rejection (43). If the proportional hazards assumption is not met, alternative parametric methods will be considered. The treatment groups will also be compared using Kaplan-Meier curves and log rank tests. Events, by severity, will be summarised descriptively. Sensitivity analyses for the primary outcome will include alternative definitions of the primary endpoint, including lung rejections of ISHLT grade 2 or higher, and ISHLT grade 3 or higher. The primary analysis will

be repeated for the per-protocol population, excluding participants with major deviations from the study protocol.

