15.4 Justification for stratification factors

The randomisation schedule is stratified for centre to balance for differences in routine practice, particularly in terms of assessing lung rejection (clinical or biopsy).

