24.2 Sample Size/Power calculations

The anticipated 12-month rejection rates for lungs in the control arm by 12 months is 80%. Published rates vary between 33-100% (43–46) depending on definition and grade of rejection and method of analysis. However, a comprehensive study of regular transbronchial biopsies in 299 lung transplant patients showed a cumulative incidence of rejection (≥grade A1) of 91.7% in the first 12 months and (≥grade A2) of 77.9% (46).

In the SSF intestinal study, we observed a 72% reduction in biopsy-proven acute rejections from the 77% rejection rate in the control arm reducing to 22% in the with skin arm. However, as a more conservative estimate for this study, we consider a relative reduction of a third from 80% to 53.33% (corresponding to an absolute difference of 26.67%) to be clinically meaningful. 128 participants who have had a transplant are required for the analysis to achieve 90% power at a two-sided significance level of 5%. To allow for a 15% loss to follow-up or death by 12 months (76 per trial arm) 152 participants need to have been randomised and transplanted. In total, approximately 254 randomisations will be required to achieve this number and account for participants not proceeding with transplant.

Assessment of the diagnostic accuracy of the SSF compared to the current reference standard (organ biopsy) is a secondary objective of this study, and is undertaken in participants who received an SSF. Assuming approximately 80% specificity, and 90% specificity, based on previous studies, 95% confidence intervals (Wilson method) around the sensitivity, specificity, positive and negative predicted values will have a width of approximately 20-30%, depending on the observed sensitivity, specificity and event rates. A sample size of 64 participants receiving SSF and providing one-year follow-up data, an expected rejection rate of 53%, and anticipated values of 80% and 90% for sensitivity and specificity, respectively, will provide approximately 80% power (at a one-sided 5% significance level) to show that the observed sensitivity and specificity in the study are statistically significantly higher than 60% and 70%, respectively.

Since the proposed mechanistic sub-studies are intended to be hypothesis generating, no formal sample size calculations have been performed.

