24.13 Level of Statistical Significance

All principal analyses will be performed at the 2-sided 5% significance level.

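### The supportive log-rank test in section 24.5 carries no centre term although randomisation is stratified by centre; stating that it is stratified by centre costs almost nothing

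*Protocol*

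**What the plan says.** Section 15.3 allocates 1:1 in permuted blocks of varying size, stratified by recruiting centre and nothing else. Section 15.4 gives the reason: "to balance for differences in routine practice, particularly in terms of assessing lung rejection (clinical or biopsy". There are five centres (section 10).

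Section 24.5 takes the primary result, an absolute risk difference at 12 months, from a mixed-effects Cox model of time to first lung rejection, "adjusted for centre as a random effect". It then adds: "The treatment groups will also be compared using Kaplan-Meier curves and log rank tests". The text does not say whether the log-rank tests are stratified by centre. Section 24.13 sets the level: "All principal analyses will be performed at the 2-sided 5% significance level".

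Two later sections borrow these methods. Section 24.6 applies them to transplanted-lung and patient survival, and section 24.8 to the composite of rejection, graft failure and death.

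**The concern.** The factor used to stratify is one the protocol itself expects to change how often the primary event is detected. Sections 8.1 and 16.8 point the same way: only some centres do surveillance biopsies, and the decision to biopsy follows local practice.

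When arms are balanced within centres, centre differences largely cancel from the treatment contrast. An unstratified log-rank test takes no credit for this. Its variance estimate is too large for the design, so it rejects too rarely under the null. It also compares arms pooled over centres with different hazards, which pulls the apparent effect towards no difference. The result is a conservative test with less power.

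What is at stake is limited but practical. The log-rank is the only other between-arm test of the primary endpoint named in 24.5. If proportional hazards fails, the section offers only unspecified parametric alternatives. A log-rank p-value that disagrees with the Cox result merely because it omits centre would confuse the reading of the trial.

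**Working it through.** **1. Reproduce the planned size.** Inputs from 24.2 and 24.13: 80% against 53.33%, two-sided 5%, 90% power. With pooled variance and no continuity correction:

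n per arm = [1.960·√(2·0.6667·0.3333) + 1.2816·√(0.80·0.20 + 0.5333·0.4667)]² / 0.2667² = (1.307 + 0.819)² / 0.0711 ≈ 63.6, so 64 per arm.

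This matches the protocol: "128 participants who have had a transplant are required for the analysis to achieve 90% power". Section 24.2 then inflates: "To allow for a 15% loss to follow-up or death by 12 months". 64/0.85 = 75.3, so 76 per arm and 152 in total. Both figures reproduce.

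**2. Effect on the hazard scale.** HR = ln(1 − 0.5333)/ln(1 − 0.80) = 0.762/1.609 = 0.474. A log-rank test with 128 patients then has about 93% power if centres are identical. That is above 90% because event times carry more information than two proportions.

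**3. Assumed between-centre spread.** The protocol gives none, so I took an SD of the log hazard from 0 to 1.0. Around an 80% control risk, centres one SD below and above have risks 1 − 0.2^exp(∓SD):

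| SD | one SD below | one SD above |
|---|---|---|
| 0.25 | 71.4% | 87.3% |
| 0.5 | 62.3% | 93.0% |
| 0.75 | 53.2% | 96.7% |
| 1.0 | 44.7% | 98.7% |

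**4. The two tests.** With p the proportion of those at risk who are in the intervention arm at each event, U = Σ(x − p) and V = Σp(1 − p). The unstratified test is Z = U/√V over all patients. The stratified test is Z = ΣU_k/√ΣV_k, with U_k and V_k computed within centre k.

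**5. Simulation of the log-rank tests.** 128 patients, five centres of equal expected size, permuted blocks of 2, 4 or 6 within centre, exponential times censored at 12 months, normal centre effects; 8,000 trials per setting.

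| SD | Power, unstratified | Power, stratified | Difference (points) | Type I error, unstratified | Type I error, stratified |
|---|---|---|---|---|---|
| 0 | 93.4% | 92.9% | −0.5 | 5.3% | 5.3% |
| 0.25 | 91.8% | 92.4% | 0.6 | 4.7% | 5.0% |
| 0.5 | 88.3% | 90.8% | 2.5 | 4.0% | 5.0% |
| 0.75 | 82.5% | 90.7% | 8.2 | 3.0% | 5.2% |
| 1.0 | 73.4% | 89.5% | 16.1 | 2.3% | 5.5% |

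Monte Carlo error is about 0.2 to 0.5 points. A separate simulation, also with 128 patients and five centres, gave unstratified against stratified power of 88/91%, 82/91% and 74/90% at SD 0.5, 0.75 and 1.0. Its unstratified type I error was 3.6%, 2.9% and 1.6%, and stratifying cost about 0.3 points with identical centres.

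**6. The primary model under the same conditions.** Mixed-effects Cox with a Gaussian centre effect, 1,500 trials per setting, Monte Carlo error about 0.6 to 0.7 points on power:

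| SD | Power | Type I error |
|---|---|---|
| 0 | 93.1% | 5.1% |
| 0.25 | 92.1% | 5.9% |
| 0.5 | 91.2% | 5.5% |
| 0.75 | 90.8% | 5.5% |

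This is level with the stratified log-rank. The run at SD 1.0 failed numerically, so nothing is claimed there. The model was tested through its treatment coefficient, not through the risk difference derived from it.

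**The case against.** The strongest reply is that the log-rank test is only supportive, that 24.5 does not call it unstratified, and that 24.1 leaves detail to a SAP that is not at hand. Much of this stands. The primary analysis does use the stratification factor, and a SAP may already stratify the test. What remains is that 24.5 names the centre term for the Cox model and not for the test in the same paragraph, so a plain reading gives an unstratified test.

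A second reply is that the larger losses come from assumed spreads. That also stands. A reader might take the 33–100% in 24.2 as the spread between centres. It is not: the protocol attributes that range to differing definitions, grades and methods across published studies. A spread of 0.5 or more can be reached by assumption. If two of five centres detected 91.7% (the figure in 24.2 for regular biopsy, grade A1 or higher) and three detected 60%, the SD would be [ln(−ln 0.083) − ln(−ln 0.40)]·√(0.4·0.6) = (0.912 + 0.087)·0.490 ≈ 0.49. With 40% in place of 60% it would be (0.912 + 0.672)·0.490 ≈ 0.78. These are illustrations, not facts about the five centres.

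A reader might also infer that a random effect for five centres is itself a fault, because its variance may be estimated as zero and centre would then drop out. With five units the variance is indeed poorly estimated. In simulations with 152 patients and 20% mortality, near-zero estimates occurred in about 34% to 41% of trials at SD 0.2. They occurred in none of 1,400 trials with centre risks of 33–99%. Centre drops out mainly when centres barely differ, and then little is lost. Centre as a fixed effect did no better: type I error was 6.7%, 6.4% and 6.0% at SD 0.25, 0.5 and 0.75, against 5.9%, 5.5% and 5.5% for the planned model. A centre-stratified Cox model would also complicate the absolute risk difference, which would have to be averaged over five baseline hazards. Random, fixed or stratified centre is a trade-off there.

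**Conclusion.** The point holds for the log-rank test and only for it. Run without centre, the test is conservative to a degree that depends on a between-centre spread the protocol does not state: negligible at an SD of 0.25 or below, about 2.5 to 3 power points at 0.5, 8 to 9 at 0.75 and 16 at 1.0, with type I error falling from 5% to about 2%. These figures assume equal expected centre sizes, exponential times, proportional hazards with HR 0.474, and 128 patients with no loss before 12 months.

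The documents do not support the stronger inference that the primary comparison loses power or validity. The planned Cox model adjusts for centre and kept about 91–93% power and 5–6% type I error at SDs of 0 to 0.75. Severity is minor.

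**What to change.** In section 24.5, replace the unqualified log-rank tests with a log-rank test stratified by centre. Sections 24.6 and 24.8 then inherit the wording for lung survival, patient survival and the composite. Leave the mixed-effects Cox model as the primary analysis.

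The cost is one line of text, and about 0.3 to 0.5 points of power for the supportive test if centres turn out not to differ. Sample size, data collection and the primary estimate are unchanged. If the SAP already stratifies the test, the protocol wording only needs to be brought into line with it.

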6 TRIAL SYNOPSIS

Full Trial Title:	rial Title: Efficacy and mechanism of sentinel skin flap reduction of solid		
	organ (lung) transplant rejection: A randomised controlled trial		
Short Title:	Sentinel Skin flap in Lung Transplant RCT		
Trial Acronym:	SENTINEL		
Trial Design:	SENTINEL is a multicentre, paralle open-label RCT.	I group, two-arm, superiority,	
Trial Participants/Target Population:	Adults (aged 18 years or over) on the waiting list to receive a lung transplant (single or bilateral and including those in combination with other organs) where offered a simulatnaeous lung and skin transplant		
Eligibility criteria:	Inclusion: 1. Intended recipient of a lung transplant 2. Aged 18 years or over 3. Capable of giving informed consent Exclusion: 1. Any significant disease or disorder which, in the opinion of the Investigator, may either put the participants at risk because of		
	participation in the study, or may influence the result of the study, or the participant's ability to comply with study procedures 2. Severe peripheral vascular disease with no vessels available for inset of the skin flap		
No. of trial arms 2			
Intervention Lung transplant with sentinel skin flap transplant		flap transplant	
Comparator Lung transplant			
Planned Sample 152 participants (76 per trial arm) Size:			
Planned Recruitment Period	36 months		
Target no. of centres:	5 NHS cardiothoracic transplant centres in the UK		
Follow-up duration:	Each participant will be followed-up for 12 months from the point of transplantation.		
	Objective	Outcome Measure	
Primary objective	To assess the efficacy of the	Lung rejection events in the first	
and outcome	sentinel skin flap (SSF) at	12 months, defined by clinical	
measure	reducing rates of acute lung	criteria diagnosis and/or biopsy	
	rejection by 12 months post- transplantation	diagnosis of rejection (ISHLT grade A≥1 for lung)	
		 TCOME MEASURES section of the ives and outcome measures.	

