16.10 Treatment of rejection

Acute rejection of the lung will be detected and treated according to established practice at the participating transplant centre. If rejection in either skin or lung is confirmed by clinical findings or pathology (BANFF grade>1 skin and ISHLT grade A>1 for lung) this will be recorded. Decision on instituting treatment will be at the discretion of the local care team. Treatment given, treatment date and outcome of treatment for rejection will be recorded. Normal local transplant follow-up protocols will continue with the addition that the skin flap will also be biopsied whenever the lung is biopsied.

The usual treatment of biopsy proven acute rejection of the SSF for Banff Grade 1 rejection will be a single 500mg dose of intravenous methylprednisolone with correction or escalation of daily immunosuppression if required, and for Banff Grade 2-4 rejection, is 3 daily doses of 500mg intravenous methylprednisolone with escalation of daily immunosuppression if required. However, any such treatment is at the determination of the clinical relevance by the local transplant team.

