*sites will take lung biopsies in accordance with local site practice; clinical diagnosis of lung rejection may be used in place of biopsy-confirmed rejection where this is also local site practice.

18.2 Sample handling for standard of care samples and trial-specific samples to be analysed in local Trust's laboratories

Standard of care samples and trial-specific samples to be analysed in local Trust laboratories will be taken and processed by laboratories in accordance with local site practice. This includes labelling of samples with standard patient identifiers. Results will be reported back in the usual way according to local practice and accessed by the site research team, and entered into the study database.

Sample Type	Time point	Test(s) to be undertaken on the sample
Lung biopsy	Upon suspicion of rejection, and when taken for monitoring as standard of care	Biopsy will be analysed by local pathology laboratory for signs of rejection. Results will be reported back on histopathology report.
Skin biopsy	Upon suspicion of rejection, and at baseline, 3, 6 and 12 months.	Biopsy will be analysed by local pathology laboratory for signs of rejection. Results will be reported back on histopathology report.

Other samples required for routine clinical follow-up following transplantation will be taken and processed by local Trust laboratories as required e.g. blood samples, broncho-alveolar samples, sputum samples.

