24.8 Additional analyses

A supplementary analysis, using the approaches for the primary outcome, will be run using a composite outcome of rejection free survival, whereby lung rejection (ISHLT A grade 1 or higher), graft failures (biopsy BANFF grade \geq 1) and death are counted as events. As participants can have recurrent lung or skin rejection events, an exploratory analysis of the ordered multiple events will be undertaken using the Prentice, Williams and Peterson total time models (44). Visual representation of recurring events will also be presented.

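### The rejection-free survival composite counts lung rejection by biopsy grade alone, so it can omit clinically diagnosed rejections that the primary outcome counts

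*Protocol*

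**What the plan says.** **Primary outcome.** Section 24.5 defines it as the "absolute difference in rejection rates (clinical or biopsy) at 12 months post randomisation". The synopsis (section 6) gives two routes, "criteria diagnosis and/or biopsy", and attaches the grade to the second of them: "diagnosis of rejection (ISHLT grade A≥1 for lung").

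**Where the grade belongs.** Section 16.10 has the same structure, with rejection "confirmed by clinical findings or pathology (BANFF grade>1 skin and ISHLT grade A>1 for lung"). The grade goes with pathology, and clinical findings are a separate route. (The inequality there differs from the synopsis. That needs reconciling but is a separate matter.)

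**Biopsy is optional.** Section 16.8 leaves the decision to biopsy the lung to local practice. The footnote to Table 4 (section 18.1) says that "clinical diagnosis of lung rejection may be used in place of biopsy-confirmed rejection where this is also local site practice". Section 15.4 stratifies by centre because of "differences in routine practice, particularly in terms of assessing lung rejection (clinical or biopsy").

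**Composite.** Section 24.8 combines "lung rejection (ISHLT A grade 1 or higher"), graft failure and death.

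**Sensitivity analyses.** Section 24.5 lists "alternative definitions of the primary endpoint, including lung rejections of ISHLT grade 2 or higher, and ISHLT grade 3 or higher".

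**Timing.** Section 24.6 states that every suspected rejection in the first three months is diagnosed by biopsy. Sections 16.8 and 18.1 contain no such requirement.

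**The concern.** An ISHLT grade exists only where lung tissue has been read. A rejection diagnosed clinically without a biopsy has no grade and cannot meet a definition written as a grade.

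The composite adds graft failure and death to the primary endpoint, so a reader expects it to contain every rejection that the primary endpoint contains. As written it need not. A participant with a clinical rejection could stand as rejection-free in an analysis named for that state.

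The grade 2 and grade 3 analyses have a related but weaker problem. They raise the histological threshold and remove the clinical route in one step. If they disagree with the primary result, the reader cannot tell whether severity or method of diagnosis is the reason. Centres are expected to differ in method, so the disagreement could also vary by centre.

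**Working it through.** **1. The plan's own figure.** Inputs from section 24.2: p1 = 0.80, p2 = 0.5333, two-sided 5%, 90% power, 15% loss.

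n per arm = [1.960 × √(2 × 0.6667 × 0.3333) + 1.282 × √(0.80 × 0.20 + 0.5333 × 0.4667)]² / 0.2667² = 63.6, rounded up to 64, so 128 in total.

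64 / 0.85 = 75.3, rounded up to 76 per arm, so 152.

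Both stated figures reproduce. They rest on the primary endpoint, so this point does not touch them.

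**2. Records read against the text.** The records are placed at month 5, after the period in which section 24.6 says that all suspected rejections are biopsied.

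| Record at month 5 | Primary (24.5) | Composite, lung rejection (24.8) | Grade ≥2 (24.5) |
|---|---|---|---|
| Biopsy A2 | event | event | event |
| Biopsy A1 | event | event | no event, as intended |
| Clinical diagnosis, biopsy also taken and graded A2 | event | event | event |
| Clinical diagnosis, no biopsy | event | definition not met | definition not met |

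Only the last row is at issue. If that participant later has a graded biopsy, the composite still counts a rejection, but dates it later than the primary analysis does.

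**3. Illustration of size.** Let f be the share of participants with rejection whose every rejection in the 12 months is clinical-only. The protocol does not give f, so the range below is an assumption. The composite's rejection component is then risk × (1 − f). With f equal in both arms:

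| f (assumed) | Control | Flap arm | Difference (points) |
|---|---|---|---|
| 0 | 80.0% | 53.3% | 26.7 |
| 10% | 72.0% | 48.0% | 24.0 |
| 20% | 64.0% | 42.7% | 21.3 |
| 30% | 56.0% | 37.3% | 18.7 |
| 40% | 48.0% | 32.0% | 16.0 |
| 50% | 40.0% | 26.7% | 13.3 |

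The relative reduction stays at one third throughout (for example 42.7 / 64.0 = 0.667). The absolute difference, which is the effect measure in section 24.5, shrinks in proportion to f.

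These figures describe one component of the composite. Deaths and graft failures still count, so the whole composite may be larger or smaller than the primary endpoint. If section 24.6 holds, anyone with a rejection in the first three months has a biopsy for it, which keeps f down. Surveillance biopsies, which section 8.1 says some centres take, would also lower it.

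**The case against.** **The composite wording may be shorthand.** The parenthesis in section 24.8 resembles the synopsis, where the same grade stands beside the clinical route, and section 24.8 says that the approaches used for the primary outcome apply. That reading is possible. But the approaches most naturally mean the analysis methods, and the graft-failure component next to it is also tied to a biopsy grade. The literal reading is therefore biopsy-only. If shorthand was meant, one phrase settles it.

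**Handling of ungraded events is normal analysis-plan content.** This stands in part. A reader might infer that the protocol scores clinical-only rejections as event-free in the grade-based analyses. That is the default result of a literal time-to-event reading, but no rule says so. The complete-case approach in section 24.4 and the censoring in section 24.14 could lead to exclusion or censoring instead. What the protocol does fix is the definition of the composite event, and that definition does not match the primary outcome.

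**A histology-only severity endpoint is legitimate.** This stands. In an open-label trial, a graded endpoint is a reasonable check on the less objective clinical diagnosis. A reader might conclude that clinical events should be added to the grade 2 and grade 3 analyses. The documents do not require it, and doing so would put events of unknown severity into a severity endpoint.

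**Bias in favour of the flap.** A reader might infer that flap recipients would have fewer lung biopsies, because a skin biopsy is always taken, and so would appear to have less graded rejection. Table 2 in section 16.8 sets no lung-biopsy rule that differs by arm, and the skin biopsy is additional to any lung biopsy. A rash also triggers further investigation (sections 16.8 and 17.4), which could push the other way. Neither the existence nor the direction of such a bias can be derived from the protocol.

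**Conclusion.** The point holds for the composite. Taken literally, section 24.8 leaves out lung rejections that are diagnosed clinically and not biopsied, although the primary outcome counts them, so the composite can contain fewer rejection events than the endpoint that it is meant to widen. If the three-month statement in section 24.6 is accepted, this mainly concerns months 3 to 12.

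The size is unknown. The range in the working rests on an assumed clinical-only share, taken as equal in both arms, and on the planning rates in section 24.2.

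For the grade 2 and grade 3 analyses the finding is narrower: they are acceptable as biopsy-graded checks, but they should be named as such, because they alter ascertainment as well as the threshold. All the analyses concerned are sensitivity or supplementary ones. The primary analysis and the sample size stand.

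**What to change.** - **Section 24.8:** replace "lung rejection (ISHLT A grade 1 or higher") with: lung rejection as defined for the primary outcome (clinical, or biopsy ISHLT A≥1). If a biopsy-only composite is intended, say so and name it accordingly.
- **Section 24.5:** keep the grade 2 and grade 3 analyses, label them biopsy-graded, and say that they change the method of ascertainment as well as the severity threshold.
- **Reporting:** beside those analyses, show the number of ungraded, clinical-only rejections by arm and centre, so that a reader can see how many events the graded definitions cannot capture.

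The cost is a few words in two sections and one additional table row. Section 17.3 already collects the method of diagnosis and the biopsy results for each rejection event, so no new data are needed. The wording should be settled before comparative data are seen.
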